TITLE:

A Placebo-controlled, Double-blinded, Randomized Pilot Study of Bupivacaine Liposome Injectable Suspension (EXPAREL) for Minimally Invasive Supracervical Hysterectomies Postsurgical Analgesia

Unique Protocol ID: 2018-0-12

Document Date: December 12, 2019

Protocol Description

All patients who are scheduled for a robot-assisted or traditional laparascopic supracervical hysterectomy will be identified in the beginning of the week (Sunday) through the OR scheduler. All patients go to pre-admission testing, where they meet with a nursing staff who will coordinate their blood work and take a history. The co-investigators will be able to prescreen them in this fashion and on the day of the surgery confirm that they are eligible for the study.

After obtaining informed consent, participants will be assigned to the intervention or placebo group randomly. Randomization will be performed based computer-based random number generator (www.randomizer.org) which would generate two sets of random numbers containing 26 numbers from 1 to 52 with each number in a set remaining unique, which will be given to the pharmacy assistant director. The master list will be only accessible by pharmacy personnel. Hospital pharmacy staff will prepare the numbered package of either Exparel or normal saline (based on the randomization) in bubbled wrapped amber bag that will be given to the resident/attending who will proceed to inject the given medication during the prepping. Unlike normal saline which will be used as placebo, EXPAREL is milky in color, therefore to ensure adequate blinding of study investigators and surgeons an independent resident will unpack the package prior to the surgery and administer it to the patient in the absence of study investigators and surgeons during the prepping. All OB-GYN residents will be instructed about the proper injection procedure prior to the start of the study. All resident are equally capable, however senior residents (PGY3/PGY4) are assigned to do hysterectomies (a total of 12 residents). We expect performance bias but will rehearse with a model cervix in the simulation lab in order to diminish it. Only the pharmacy staff and independent residents will have access to the random generated list; all other staff including the investigators, surgeons, anesthesiologists, and nurses as well as patients will be kept blinded to the assigned treatments.

Subjects in the intervention arm will receive paracervical block with 20 ml of extended-release liposomal bupivacaine (EXPAREL) at the 4 and 80'clock positions. Subjects in the placebo arm will receive paracervical/intracervical block with 20 ml of saline at the 4 and 8 o'clock positions. In both study arms the injection will be administered preoperatively.

Post operative pain management will be the same for both study groups. Immediately after surgery in the recovery room they will be able to receive ketorolac 30mgIV and/or acetominophen 1000mg IV, and if needed narcotics (as requested by the patient). This will all be recorded in the anesthesia record which is accessible to the co-investigators. Robot-assisted and traditional laparoscopic supracervical hysterectomy are ambulatory cases and we expect same day discharge. At home or in the hospital, all study participants will have oral acetaminophen 650mg q4-6 hr and NSAIDS 600mg q4-6 hours, as needed. If needed they will also have percocet 5-325mg q4-6 hours, the first dose of which will be recorded as the median time to narcotics.

Post operative pain management for both groups will include a combination of oral or parenteral nonsteroidal anti-inflammatory medications, and oral or parenteral opioids to be used as needed. Since most patients who undergo minimally invasive hysterectomy are discharged few hours after the surgery, data regarding the time, type and dose of postoperative analgesics used by the patient will be collected by providing the patient with a pain diary before discharge. Patient will be instructed to record use of any analgesics (including NSAIDS) for 72 hours whether the analgesic was prescribed by the surgeon or was taken at patient's own discretion. These data regarding the time, number and type of breakthrough analgesia will be used for evaluation of median time to first

break through opioid use and total opioid analgesic requirement.

The severity of pain will be assessed preoperatively in the holding area, at the time of PACU arrival, and at 12, 24, and 48 hours postoperatively using a numeric rating scale (NRS) from 0 to 10 with 10 being the worst pain the patient has ever experienced. The first two assessments will be performed in the hospital by the principal investigators and the remaining assessments will happen through a phone conversation with the patient after discharge from hospital. The NRS has been found to be a simple and valid alternative to the visual analog scale, and has been validated by Paice and Cohen in 1997. Based on this study which examined the validity of a verbally administered NRS using convergence methods, the correlation between the VAS and the NRS was strong and statistically significant ($\mathbf{r} = 0.847$, p < 0.001), supporting the validity of the verbally administered NRS. Type of pain (characterized as sharp, dull, stabbing, aching), location of pain (categorized as right upper quadrant, epigastric, left upper quadrant, right lumbar, umbilical, left lumbar, right iliac, hypogastric, left iliac) and radiation of pain will also be evaluated and recorded.

Based on the available evidence EXPAREL's adverse effects includes QT interval prolongation. The long QT prolongation syndrome usually does not manifest in any symptoms however one reported symptom is fainting, and if left persistent can lead to seizure activity and or death. To assess the incidence and severity of adverse events, patients' heart activity will be monitored during the surgery and any abnormal findings in the electrocardiogram pattern will be recorded. Additionally, before patient's discharge from hospital, the investigator will seek information on adverse event of the intervention by specific questioning and, as appropriate, by examination. Questions will include, do you feel faint and/or dizzy, do you have difficulty breathing. Information on all adverse events will be recorded immediately and the clinical course of each event will be followed until resolution, stabilization, or until it has been determined that the study treatment or participation is not the cause. Any adverse event that occurs after patient discharge and is considered to be possibly related to the study intervention will also be recorded. Adverse events can include readmission, signs and symptoms of infection, and bleeding.

The Data Safety and Monitoring Board (DSMB) will include 3 doctors, who are independent of the study. Members of DSMB will meet every 2 months at Maimonides hospital to carry out a regular assessment of the number and type of serious adverse events. They will report their findings or recommendations to the principal investigator and representatives from Maimonides Institutional Review Board (IRB). The DSMB will recommend whether to continue the study or stop it early considering the objectives of the study and subjects safety.

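### The protocol gives two incompatible rules on who may see the randomization list and names the injector inconsistently, which puts the surgeons' blinding at avoidable risk

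*Protocol*

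**What the plan says.** Everything on this point stands in the randomization and blinding text of the Protocol Description.

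- **Access to the list, first statement:** "The master list will be only accessible by pharmacy personnel".
- **Access to the list, closing statement:** "Only the pharmacy staff and independent residents will have access to the random generated list". The same sentence goes on: "all other staff including the investigators, surgeons, anesthesiologists, and nurses as well as patients will be kept blinded to the assigned treatments".
- **Injector, first statement:** the numbered package "will be given to the resident/attending who will proceed to inject the given medication during the prepping".
- **Injector, next sentence:** because EXPAREL looks milky and saline does not, "to ensure adequate blinding of study investigators and surgeons an independent resident will unpack the package prior to the surgery" and is to "administer it to the patient in the absence of study investigators and surgeons during the prepping".
- **Residents:** "All OB-GYN residents will be instructed about the proper injection procedure prior to the start of the study". The text adds that "senior residents (PGY3/PGY4) are assigned to do hysterectomies (a total of 12 residents" in all).

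The text does not say what makes a resident independent.

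**The concern.** The trial is titled double-blinded, but the two products can be told apart by sight. The protocol therefore protects the blinding of investigators and surgeons by controlling who handles the product and who sees the assignments. On both matters it gives two answers.

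List access matters more. Whoever opens a package learns the product for that one patient, and the design accepts this. Whoever holds the list also learns what patients not yet treated will receive. An injector has no stated need for that, since pharmacy prepares and numbers each package. Senior residents also operate, so a resident who has looked at the list could later be in theatre as a surgeon for a participant whose arm is already known to them. The protocol says that surgeons are to be kept blinded.

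**Working it through.** No figure is involved, so the check sets the statements side by side.

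1. **Are the two list rules compatible?** The first admits pharmacy personnel and nobody else. The closing one admits pharmacy staff and independent residents and nobody else. A resident is excluded by the first and admitted by the second, so both cannot be followed.

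2. **Could they concern two different lists?** The text describes one randomization output, the number sets from the web generator that go to the pharmacy assistant director. It never separates a master list from a second list. Even if there were two, the random generated list would be the generator's own output, and that is what fixes the assignments. Access to it would still show future assignments.

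3. **Does any stated task need residents to have the list?** Pharmacy prepares a numbered package according to the randomization and hands it over wrapped in an amber bag. The resident unpacks it and injects. Neither step needs the list.

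4. **Are the two injector statements compatible?** The first allows a resident or an attending. The second names an independent resident only and requires surgeons and investigators to be absent. An attending who is a surgeon or investigator could not inject without breaking the absence rule and the closing blinding rule. The second sentence gives its reason, so it appears to be the intended rule. The word *attending* is then left over.

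5. **Does anything separate list holders from later operators?** The absence rule implies that the injector is not that same patient's surgeon. It says nothing about later patients. The closing sentence states the aim that surgeons stay blinded, but it does so in the same breath as it gives the list to independent residents. Senior residents do hysterectomies, *independent* has no definition, and no rule bars a resident who has seen the list from operating on a later participant.

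6. **How far can this reach the outcomes?** The principal investigators conduct the preoperative and PACU-arrival pain assessments, and the later ones are made by phone. In each, the patient gives the 0 to 10 score. Analgesic use after discharge comes from the patient's own diary. Patients are to be blinded. An assessor who knew the arm could still influence an answer, but the protocol does not say that any resident or attending makes these assessments.

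**The case against.** The strongest reply is that the text, read as a whole, shows what is meant. The two injector sentences are adjacent and run from general to specific. The second explains itself, and the closing sentence repeats that surgeons and investigators stay blinded. The plain sense of *independent* here is someone who is neither an investigator nor a surgeon in the study. Giving such residents the list does not show it to investigators or surgeons. Harm would need a further step: disclosure, or a resident with list access operating later. The document states neither.

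Much of this stands. The injector mismatch is mainly a drafting remnant and is the lesser half of the point. The further step is indeed needed, so this is a risk only.

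It does not answer the list conflict. Two exclusive rules that name different groups cannot be reconciled by reading from general to specific. Nor does the plain sense of *independent* say whether a resident may inject for one patient and operate on the next, when senior residents are the ones assigned to these operations.

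A reader might be tempted by three stronger readings that the document does not support:

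- **That blinding is broken.** This would need someone required to be blinded actually to see the product or the list. The text leaves room for that but does not direct it.
- **That enrolment could be selective.** Co-investigators prescreen patients and confirm eligibility. Residents have no stated part in enrolment, so knowledge of upcoming assignments is not tied to who enters the trial.
- **That pain ratings are made by someone who knows the arm.** Patients score their own pain, and no unblinded person is named as assessor.

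**Conclusion.** The protocol contradicts itself on list access, and nothing in it resolves the contradiction. It also names the injector inconsistently, though there the intended rule can be recognized. The textual conflict is certain; its consequence is only possible. If the wider list rule is followed, residents see assignments of patients not yet treated without needing to, and one of them could operate on a later participant while knowing the arm.

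The size of any effect on pain or opioid results cannot be derived from the document. The conclusion rests on two readings: that the master list and the random generated list are the same output, or at least both reveal assignments; and that residents who inject may come from the pool that operates, which the text does not exclude. It should be fixed, because the correction is small and the safeguard it restores is one the protocol itself relies on.

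**What to change.** Two wording changes in the randomization and blinding text of the Protocol Description:

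(a) In the closing sentence, restrict list access to pharmacy staff. State that the injecting resident receives only that patient's numbered package, will know that patient's product on opening it, and does not disclose it. Keep the rest of the sentence on who remains blinded.

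(b) Where the package is handed over, replace the resident-or-attending wording with *independent resident*. Define this as a resident who is not a study investigator, is not on that patient's surgical team, and does not collect that patient's pain assessments.

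The cost is rostering: for each case the injecting resident must differ from the operating resident and from the pain assessor. The protocol says that all OB-GYN residents will be trained in the injection, so the injector need not be one of the senior residents. It does not say how many residents are available on a given day. The last part of the definition, on pain assessments, goes beyond reconciling the text; it is a precaution that the protocol does not now contain.

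One limit remains. The absence rule covers only investigators and surgeons, while the closing sentence also promises blinding of anesthesiologists and nurses. These edits do not supply a procedure for those two groups.

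### The step that hides the milky drug once the package is opened covers only investigators and surgeons, while the blinding statement also names anesthesiologists and nurses

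*Protocol*

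**What the plan says.** All of the blinding text stands in one paragraph of the Protocol, under Protocol Description, on randomization and preparation of the study drug.

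- **The visible difference.** "Unlike normal saline which will be used as placebo, EXPAREL is milky in color".
- **Concealment up to opening.** Pharmacy prepares a "numbered package of either Exparel or normal saline (based on the randomization) in bubbled wrapped amber bag".
- **Concealment after opening.** The purpose is stated for two roles: "to ensure adequate blinding of study investigators and surgeons an independent resident will unpack the package prior to the surgery". That resident is then to "administer it to the patient in the absence of study investigators and surgeons during the prepping".
- **Who is declared blinded.** Apart from pharmacy staff and the independent residents, "all other staff including the investigators, surgeons, anesthesiologists, and nurses as well as patients will be kept blinded to the assigned treatments".

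The later paragraphs on postoperative pain management say that in the recovery room patients "they will be able to receive ketorolac 30mgIV and/or acetominophen 1000mg IV, and if needed narcotics (as requested by the patient"), and that these drugs are entered in the anesthesia record. Analgesic use is also kept in a 72-hour patient diary, which serves the evaluation of time to first breakthrough opioid and of total opioid requirement. Pain is self-reported on a 0 to 10 scale. The principal investigators take the holding-area and PACU-arrival scores, and the 12, 24 and 48 hour scores are obtained by telephone.

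**The concern.** The protocol identifies the threat to the blind, a drug that can be told from placebo by looking at it, and then counters it for only part of the group it calls blinded. The title describes the trial as double-blinded. Its outcomes are either self-reported (pain) or depend on as-needed treatment (opioid timing and amount), and such outcomes are open to influence by anyone who knows the arm.

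Staff who had seen which product was injected could act on it in two ways. They could be readier to offer, or slower to offer, analgesia in the recovery room. They could also let the arm be known to the patient, or to the investigators who ask for the pain scores. A blind lost at injection cannot be restored in the analysis, so the procedure itself has to be right.

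**Working it through.** No arithmetic applies beyond the count of patients. The check compares the list of people declared blinded with the list of people whom the concealment step protects.

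**Step 1. Coverage by role.**

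| Role | Declared blinded | Required to be absent at injection | Other stated protection once the package is open |
|---|---|---|---|
| Investigators | yes | yes | none needed if absent |
| Surgeons | yes | yes | none needed if absent |
| Anesthesiologists | yes | no | none |
| Nurses | yes | no | none |

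The amber bag hides the product from everyone, but only until the resident unpacks it. No opaque syringe, sleeve, screen, drape or look-alike placebo is described. Two of the four named staff roles therefore have a promise of blinding without a measure behind it. Patients are also on the blinded list and outside the absence rule, but the protocol does not say what they could see, so the point does not rest on them.

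**Step 2. What must be true for the gap to bias a result.**

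1. Anesthesia or nursing staff are present when the drug is injected. Not stated. It is a reasonable inference from the timing during prepping, and nothing excludes them, whereas investigators and surgeons are excluded by name.
2. They can see the opened product. Not stated, and nothing prevents it.
3. The same people treat the patient in the recovery room, or they pass the information on. Not stated. The protocol does not say who gives the recovery-room drugs, and an entry in the anesthesia record does not show who decided on them.
4. There is discretion in the treatment. This is partly so. Narcotics follow the patient's request; the wording on ketorolac and acetaminophen carries no such qualifier.

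**Step 3. Which outcomes are reachable.**

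- *PACU-arrival pain score.* It is taken on arrival, and the drugs in question are given in the recovery room, so those drugs are not an evident source of bias in it. The assessor is an investigator under the absence rule. The remaining route is disclosure of the arm.
- *Pain at 12, 24 and 48 hours.* These are telephone scores planned after discharge. The main route is again disclosure to patient or assessor.
- *Time to first opioid and total opioid requirement.* Recovery-room analgesia could change when, and how much, opioid the patient asks for later. The measures remain largely patient-driven, through request and diary.

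**Step 4. Size.** Randomization uses two sets of 26 numbers, 2 × 26 = 52. Every case passes through the same opened-package step, so 52 is the largest number that could be exposed. The document gives nothing from which to estimate how many would be, or how far an outcome would shift.

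**The case against.** The strongest reply is that the protocol does commit to keeping anesthesiologists and nurses blinded, and merely leaves out how. No sentence places either role at the injection, and the staff who work in the recovery room may be different people. Those who score pain are investigators, who are shielded. The opioid data come mainly from patient requests and a patient diary. On this view the defect is one missing sentence in a pilot study.

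Much of that stands, and it limits the consequences. A reader might infer that the double blind fails for these roles in all 52 patients, that anesthesia staff control intra-operative and recovery-room analgesia, and that the PACU-arrival score is therefore biased. The documents do not support this. Presence and line of sight are inferred, intra-operative analgesia is not described, the protocol does not say who gives recovery-room drugs, and the arrival score is taken by investigators covered by the absence rule.

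The reply does not remove the mismatch. The protocol sets out its concealment step in detail and states for whom it is meant. Followed exactly as written, it leaves two declared-blinded roles without protection. That is a safeguard drawn too narrowly, and it would not ordinarily be left to a statistical analysis plan.

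**Conclusion.** The point holds as a mismatch within the protocol: the blinding statement is wider than the measure that is meant to deliver it. For anesthesiologists and nurses, nothing stated conceals a visibly milky product once it is unpacked.

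The consequence is a risk to the opioid-use and self-reported pain outcomes, not a demonstrated unblinding. It rests on the assumptions that such staff are present during prepping, that they can see the product, and that they either treat the patient afterwards or disclose the arm. Its size cannot be derived; 52 patients is a ceiling on exposure only. The patient-requested narcotics and the shielded in-hospital pain assessors reduce it.

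The gap is separate from another inconsistency in the same paragraph, where the package is one "that will be given to the resident/attending who will proceed to inject the given medication during the prepping", while an independent resident is named later. Settling who injects would leave the present gap open, although the two passages should be reconciled at the same time because the fix relies on the independent resident.

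**What to change.** Extend the concealment to every role that the protocol calls blinded:

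- Pharmacy dispenses both products in identical opaque or sleeved syringes, so that the contents cannot be seen after unpacking.
- The independent resident injects behind a visual barrier that blocks the view of anyone else present, and removes syringes and packaging before others enter.
- Any role that cannot be shielded in this way is taken off the blinded list, so that the protocol claims only the blinding it can deliver.

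There is no need to bar staff from recovery-room analgesia or from pain scoring. The first would carry a staffing cost, and the protocol gives anesthesiologists and nurses no pain-scoring task.

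The cost is small: sleeves or opaque syringes, a screen or drape, a sentence or two in the protocol, and slightly more pharmacy preparation and setup time per case. The change should be made before enrollment, or else applied to all remaining patients, since it cannot repair cases already injected.

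### Plain acetaminophen and Percocet run on the same as-needed interval with no combined limit, permitting up to 975 mg acetaminophen per interval and 5,850 mg a day

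*Protocol*

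**What the plan says.** The unnumbered Protocol Description sets drug, dose and interval for the analgesics that both arms receive after surgery.

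- **Recovery room:** "they will be able to receive ketorolac 30mgIV and/or acetominophen 1000mg IV", with narcotics on request.
- **Afterwards, at home or in the hospital:** "all study participants will have oral acetaminophen 650mg q4-6 hr and NSAIDS 600mg q4-6 hours, as needed".
- **Rescue, in the next sentence:** "If needed they will also have percocet 5-325mg q4-6 hours".
- **Setting:** the operations "are ambulatory cases and we expect same day discharge".
- **Recording:** "Patient will be instructed to record use of any analgesics (including NSAIDS) for 72 hours". The diary covers self-chosen drugs as well as prescribed ones.
- **Contact after discharge:** pain is rated at 12, 24 and 48 hours, and "the remaining assessments will happen through a phone conversation with the patient after discharge from hospital".

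The document gives no daily maximum for acetaminophen, no rule for substituting or staggering the two products, no gap between the intravenous dose and the first oral dose, and no reminder that Percocet contains acetaminophen.

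**The concern.** The two oral instructions share an active ingredient and an interval, and the word *also* makes the second an addition to the first. A patient whose pain calls for Percocet can therefore take both in every interval and still be following the protocol. No misuse is needed. Only patients who use rescue can reach the higher totals, and the trial expects rescue use, since opioid requirement is one of the things it measures.

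Nothing described in the protocol would limit the total. The diary records what was taken. The calls are described as covering the severity, type, location and radiation of pain. The adverse-event questions put before discharge ask about faintness, dizziness and breathing, and come before most home dosing. The monitoring board reviews serious adverse events every two months.

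What is at stake is participant safety, through wording that lets patients stack one drug without noticing.

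**Working it through.** The protocol states no daily total of its own, so there is no figure to reproduce. The check is dose arithmetic on the stated doses.

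**Inputs, all from the Protocol Description**
- Plain oral acetaminophen: 650 mg every 4 to 6 hours, as needed.
- Percocet 5-325 every 4 to 6 hours, if needed. Assumption: 325 is milligrams of acetaminophen and a dose is one tablet; the document spells out neither.
- Optional intravenous acetaminophen in the recovery room: 1,000 mg.

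**Per interval:** 650 + 325 = 975 mg, and 975 / 650 = 1.5.

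**Per day at full use of both:** (24 / interval in hours) × 975.

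| Interval | Doses per day | Plain alone (mg) | From Percocet (mg) | Both (mg) |
|---|---|---|---|---|
| 4 h | 6 | 3,900 | 1,950 | 5,850 |
| 5 h | 4.8 (average) | 3,120 | 1,560 | 4,680 |
| 6 h | 4 | 2,600 | 1,300 | 3,900 |

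**Reference point.** The most that the plain instruction alone allows is 6 × 650 = 3,900 mg a day. Setting (24 / t) × 975 = 3,900 gives t = 6 hours, so full use of both passes that figure at any interval shorter than 6 hours.

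**Lower rescue use on top of full plain dosing**
- One tablet a day, 4-hour dosing: 3,900 + 325 = 4,225 mg; 325 / 3,900 = +8.3%.
- One tablet a day, 6-hour dosing: 2,600 + 325 = 2,925 mg; 325 / 2,600 = +12.5%.
- Three tablets a day, 4-hour dosing: 3,900 + 975 = 4,875 mg; 975 / 3,900 = +25%.

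**First 24 hours when the intravenous dose is given**
- Oral dosing starts one interval later, 4-hourly (at 4, 8, 12, 16 and 20 h): 1,000 + 5 × 975 = 5,875 mg.
- The same, 6-hourly (at 6, 12 and 18 h): 1,000 + 3 × 975 = 3,925 mg.
- No gap, which the text allows, so a full day of oral dosing is added: 1,000 + 5,850 = 6,850 mg (4-hourly) or 1,000 + 3,900 = 4,900 mg (6-hourly).

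**The case against.** The strongest reply is that the harm has no anchor in the document. The protocol gives no safe daily maximum and none is supplied here, so the arithmetic shows only that two products add up to more than one. That stands as a limit: how far the ceiling exceeds a safe dose cannot be judged from this document. It does not remove the point. The document prescribes the same ingredient twice at the same interval without saying whether the doses add, and that is a fault in a dosing instruction whatever threshold one adopts.

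Second, both drugs are as needed. The 5,850 mg figure requires the shortest interval, full use of both and dosing round the clock. At 6-hour dosing the total only equals 3,900 mg. This is true, and it is why the figure is called a ceiling and the lower-use cases are shown.

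Third, a limit may appear on the prescription, the discharge sheet or the diary, none of which is shown. That is possible, but the protocol refers to no such limit, and the regimen it does state permits the stacking.

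Fourth, the regimen is the same in both arms and has no bearing on the trial's inference. This is correct, and it limits how serious the point is. A related caution is fair: reducing plain acetaminophen in rescue users could slightly affect opioid use, which is an outcome. The rule would apply alike in both arms, and the second option in the fix leaves acetaminophen per interval at the plain dose.

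**Conclusion.** The concern holds and should be fixed. As written, the regimen permits 975 mg of acetaminophen per interval, which is 5,850 mg a day at 4-hour dosing and 3,900 mg at 6-hour dosing, each 50% above plain acetaminophen alone. If the intravenous dose is given, the first-day ceiling is 5,875 mg or 3,925 mg with a one-interval gap, and 6,850 mg or 4,900 mg with none.

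The figures rest on reading 325 as milligrams of acetaminophen and on one tablet per dose. They describe what the text allows and not what patients will usually take, and no toxic threshold is claimed. The regimen covers hospital stays too, but the practical concern is the patient at home. This is a point of safety wording, without consequence for sample size, error rates or the comparison of arms.

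**What to change.** Add the following to the postoperative pain paragraph and to the diary instructions:

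1. Acetaminophen in Percocet and in the recovery-room intravenous dose counts toward the acetaminophen order.
2. In an interval when Percocet is taken, it replaces the plain dose, or the plain dose is cut to 325 mg so that the interval total stays at 325 + 325 = 650 mg.
3. The first oral dose comes at least one interval after the intravenous dose.
4. The combined 24-hour total does not exceed 3,900 mg (6 × 650, what the plain order already allows), or a lower figure set by pharmacy. After the intravenous dose this leaves 3,900 − 1,000 = 2,900 mg; 2,900 / 650 = 4.46, so four full doses, for a total of 1,000 + 4 × 650 = 3,600 mg.

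Also ask about total acetaminophen intake at the 12, 24 and 48 hour calls.

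The cost is a line in the protocol, a line in the diary and one question at contacts already planned, with no extra staff or visits. The downside is slightly less non-opioid analgesia for patients using maximal rescue. Cutting the plain dose to 325 mg gives up less than replacing it, so it is the milder choice if an effect on opioid requirement is a worry. The rule must be the same in both arms.
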